### Continuous endpoint

The continuous endpoint will be analyzed in a similar manner as the primary efficacy endpoint.

### Sensitivity Analyses

Similar to primary efficacy endpoint, missing PP-NRS will be imputed using the multiple imputation (MI) with analysis of covariance (ANCOVA) model. MI will be performed under missing at random (MAR) assumption.

The Week 16 data of each of the 100 complete imputed datasets will be analyzed using an ANCOVA model with treatment, randomization strata, and baseline PP-NRS value included in the model, and the SAS MIANALYZE procedure will be used to generate valid statistical inferences by combining results from the 100 analyses using Rubin's formula.

The percent change from baseline in PP-NRS will also be analyzed using MMRM without imputation. The model will include factors (fixed effects) for treatment, randomization strata, visit, treatment-by-visit interaction, and baseline PP-NRS score. An unstructured covariance matrix will be used to model the within-patient errors. Denominator degrees of freedom will be estimated using approximation of SATTERTH. The efficacy data will be set to missing after rescue medication or procedure is used or after study withdrawal. Afterwards no imputation will be made.

The MMRM model will provide baseline adjusted least-squares (LS) means at Week 16 and at other time points for each treatment group with the corresponding standard error and the confidence interval, as well as the p values for treatment comparisons. The graph of LS-mean +/- SE by visit will be provided.

Other following sensitivity analyses will be planned for the key secondary using the ANCOVA or logistic model mentioned above, as applicable:

- In FAS, using PMM-MI and including site as a factor in the ANCOVA model.
- PP analysis set, using MI for handling missing data for all key secondary endpoints.
- In FAS, the LOCF and WOCF methods for handling missing data for continuous endpoints.

- In FAS, the TF method for handling missing data for binary endpoints.
- In FAS, the Observed-Cases (OC) approach for all endpoints. No imputation for missing data at any time point.

## 2. Other Secondary Endpoints

The other secondary endpoints will be summarized descriptively.

The analysis will be based on FAS and will use MI, LOCF for the imputation of continuous endpoints and TF for categorical endpoints. The data will additionally be summarized using the OC.

- Change from baseline in PP-NRS at Week 16
- Percent of subjects achieving EASI-50 from baseline to Week 2, 4, 8, 12, 16.
- Percent of subjects achieving EASI-75 from baseline to Week 2, 4, 8, 12, 16
- Percent of subjects achieving EASI-90 from baseline to Week 2, 4, 8, 12, 16.
- Percent of subjects achieving at least 2-point reduction in vIGA score from baseline to Week 2, 4, 8, 12, 16.
- Percent of subjects achieving  $\geq 4$ - point reduction in PP- NRS from baseline at Week 2, 4, 8, 12, 16.
- Percent of subjects achieving  $\geq 3$ - point reduction in PP- NRS from baseline at Week 2, 4, 8, 12, 16.

### Time to Events Endpoints

The following endpoints are considered time to event endpoints and the analysis will be based on the FAS using OC;

- Among subjects with baseline PP-NRS  $\geq 4$ , time to achieving  $\geq 4$ -point reduction in PP-NRS from baseline
- Among subjects with baseline PP-NRS  $\geq 3$ , time to achieving  $\geq 3$ -point reduction in PP-NRS from baseline
- Time to achieving first occurrence of EASI-50 from baseline
- Time to achieving first occurrence of EASI-75 from baseline
- Time to achieving first occurrence of EASI-90 from baseline

The time to achieving is defined as:

$$(\text{first occurrence} - \text{first treatment date}) + 1.$$

If the subject does not achieve the event, then the subject will be censored at their last non-missing assessment. If a subject uses rescue medication, then the subject will be censored at their last assessment prior to use of rescue medication. Estimates of medians and quartiles with 95% confidence intervals using the Kaplan-Meier (K-M) methods and unstratified and stratified log-rank tests will be reported.

## E. Exploratory Efficacy Analysis

All exploratory efficacy analysis will be based on the FAS. Descriptive summary statistics will be provided by treatment and visit for exploratory endpoints listed below. No imputation will be utilized for missing data.

- Percent change in SCORAD from baseline at Week 2, 4, 8, 12, and 16
- Percent change in BSA from baseline at Week 2, 4, 8, 12, and 16
- Change from baseline to Week 16 in sleep loss from the SCORAD VAS
- Change from baseline to Week 16 in POEM
- Change from baseline to Week 16 in DLQI
- Change from baseline to Week 16 in Skin pain NRS
- Change from baseline to Week 16 in PtGA  
A shift table from baseline will be provided.
- Change from baseline to Week 16 in ADSS  
For item 1 and 3 a shift table will be provided to display the change from baseline. The change from baseline for item 2 will be presented descriptively.

- Change from baseline to Week 16 in ACQ-5  
A shift table from baseline will be provided for each question
- Percent of subjects achieving a PtGA score of 0 or 1 and a  $\geq 2$  point reduction from baseline at Week 2, 4, 8, 12, and 16. The assessment at each specific timepoint will be independently considered.
- Subgroup analysis of the primary efficacy endpoint as outlined in section IV.I
- Proportion of subjects maintaining responder status at Weeks 18, 20, 24 among those achieving the corresponding responder status at Week 16 and not receiving rescue therapy from Week 8 to Week of interest. The endpoint at Week 20 will not consider Week 18 status and will include subjects that do not use rescue from Week 8 to Week 20. Similarly, Week 24 will not consider responder status at Week 18 and Week 20 and will only include subjects that did not use rescue from Week 8 to Week 24. An additional analysis will be conducted without consideration of the use of rescue medication after Week 16. The following responder status will be analyzed separately.
  - EASI-50
  - EASI-70
  - EASI-90
  - vIGA score of 0 or 1
- Percent change in EASI at Weeks 18, 20, and 24 compared to Week 16 among those not receiving rescue therapy from Week 8 to Week of interest. In other words, the analysis at Week 20 will only include subjects who do not use rescue from Week 8 to Week 20.
- Percent change in SCORAD at Weeks 18, 20, and 24 compared to Week 16 among those not receiving rescue therapy from Week 8 to week of interest.

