6.6.4 Rescue Medications

Subjects who require topical corticosteroids, calcineurin inhibitors, or PDE4 inhibitor medications that could directly impact AD disease activity prior to Day 57 will be withdrawn from study drug and the study if requiring such topical therapies prior to Day 57.

Starting at Day 57, rescue medications for persistent, intolerable AD activity may be considered by the Investigator. Investigators must document evidence of continued active AD with EASI unchanged from or greater than the Baseline EASI score over 2 consecutive visits before initiating therapy. All subjects requiring rescue therapy between Day 57 (Week 8) and Day 113 (Week 16) will remain in the study and on study drug until Week 16.

After the end of treatment at Day 113 and during the follow-up phase, subjects may also initiate rescue if either the subject or investigator feels that there is persistent, intolerable AD activity.

Permitted rescue medications include low- to moderate-potency (class IV-class VII) topical corticosteroids ([Appendix 14](#)) and should be applied only to problem areas. A topical calcineurin inhibitor, topical PDE4 inhibitor (e.g., crisaborole), or low-potency topical steroid may be used on the face if affected. Subjects who require rescue therapy will be considered non-responders for all efficacy endpoints with data imputed for subsequent continuous endpoints for all time points as detailed in the Statistical Analysis Plan (SAP). Ideally, the specified medication for rescue treatment would be supplied by the clinic so that the tube could be weighed prior to administration. In addition, use of the specified medication should be recorded in the e-Diary, and the medication should be brought to clinic at subsequent visits to assess amount of medication used.

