9.4.5 Missing Data

For the primary and key secondary efficacy endpoints, the efficacy data collected after the start of rescue medication will be set to missing. All missing data up to Week 16 will be imputed using a multiple imputation (MI) technique as follows:

- Intermittent missing data will first be imputed using the Markov Chain Monte Carlo (MCMC) method implemented with the SAS PROC MI procedure and imputed datasets with monotone missing pattern will be generated. This applies to intermittent missing data prior to the intercurrent events including early termination of the study treatment as well as initiation of rescue medications.
- The monotone missing values will then be imputed with the imputation model estimated from subjects in the placebo group using the SAS PROC MI procedure with MNAR statement. This approach is based on the missing not at random (MNAR) assumption. This assumes that the missing data in

the RPT193 doses post treatment discontinuation and/or the start of rescue medication follow similar profile as the placebo group.

- Response status (Yes, No) will be derived from the imputed scores in each MI datasets for binary endpoints. The results of the multiple MI datasets will then be combined into a single analysis using PROC MIANALYZE.

As a sensitivity analysis, all missing continuous data up to Week 16 will also be imputed by using last observation carried forward (LOCF). Missing data for responder endpoints will be imputed as treatment failures (TF). Additional sensitivity analyses under different assumptions for missing data handling may be explored in the SAP.

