## 2. Missing EASI, vIGA and PP-NRS

Missing data will be imputed for the primary and secondary endpoints, which includes the composite EASI score, vIGA and PP-NRS for the 16-week treatment period. Assessment after the use of rescue will be set to missing prior to any imputation. No imputation is planned for the follow-up period. The following missing data techniques will be utilized:

**Last Observation Carried Forward (LOCF):** All missing data up to Week 16 will be imputed by the last observed value carried forward for any subsequent missing values. For patients with only baseline value, the baseline value will be carried forward to Week 16. This will be applied to the continuous endpoints of composite EASI score and PP-NRS.

**Worst Observation Carried Forward (WOCF):** All missing data up to Week 16 will be imputed by the worst observed value carried forward for any subsequent missing values. For patients with only baseline value, the baseline value will be carried forward to Week 16. This will be applied to the continuous endpoints of composite EASI score and PP-

NRS.

**Treatment Failures (TF):** All missing binary endpoint data up to Week 16 will be imputed as failure. This will be applied to key secondary binary endpoints of EASI-75, responder and vIGA score of 1 or 0, and other secondary endpoints of EASI-50, EASI-90, at least 2-point reduction in vIGA, at least 3-point/4-point reduction PP-NRS.

**Observed Cases (OC):** No missing data will be imputed. All observed data will be included. To reiterate, data after the rescue medication will be set to missing.

**Multiple Imputation (MI) under MAR:** Missing continuous endpoints of EASI, and PP-NRS will be imputed using the multiple imputation (MI) with analysis of covariance (ANCOVA) model as the primary analysis for time-points at which no value is observed. MI will be performed under missing at random (MAR) assumption. The MI is a simulation-based approach where missing values are replaced by multiple Bayesian draws from the conditional distribution of missing data given the observed data and covariates, creating multiple completed data sets.

For the EASI assessment, all missing scheduled visits as outlined in the protocol will be imputed. For the PP-NRS assessment, all missing weekly visits will be imputed.

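### SAP VI.E states no post-rescue rule for the exploratory efficacy endpoints through Week 16, although Protocol 6.6.4 sets one for all efficacy endpoints

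*SAP*

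**What the plan says.** - **Protocol 6.6.4** sets the broad rule: "Subjects who require rescue therapy will be considered non-responders for all efficacy endpoints with data imputed for subsequent continuous endpoints for all time points". It leaves the detail to the SAP. It also keeps these subjects under observation: "All subjects requiring rescue therapy between Day 57 (Week 8) and Day 113 (Week 16) will remain in the study and on study drug". Anyone needing such topical treatment earlier "will be withdrawn from study drug and the study if requiring such topical therapies prior to Day 57".
- **Protocol 9.4.5** is narrower: "For the primary and key secondary efficacy endpoints, the efficacy data collected after the start of rescue medication will be set to missing". Protocol 9.4.4 asks only for descriptive statistics on exploratory endpoints.
- **SAP IV.D.2**, headed for EASI, vIGA and PP-NRS, opens: "Missing data will be imputed for the primary and secondary endpoints, which includes the composite EASI score, vIGA and PP-NRS for the 16-week treatment period". The instruction to blank post-rescue assessments stands in that section. The estimand table (SAP II.A) names the same three scores.
- **SAP VI.E** covers the exploratory endpoints in the FAS: "Descriptive summary statistics will be provided by treatment and visit for exploratory endpoints listed below. No imputation will be utilized for missing data". PtGA response (score 0 or 1 with at least a 2-point drop) is judged at each visit on its own. Rescue appears in VI.E only for the Week 18, 20 and 24 durability endpoints.
- **SAP I.C** lists two changes from the protocol, the region stratum and the CCL17/22 subgroups. Rescue handling is not one of them.

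**The concern.** The protocol hands the SAP the job of spelling out rescue handling for all efficacy endpoints, and the SAP does so for three scores. Rescued subjects go on being assessed to Week 16, so their SCORAD, BSA and patient-reported scores will exist, and a programmer has to decide what to do with them. If they are tabulated as observed, improvement on a topical corticosteroid, calcineurin inhibitor or PDE4 inhibitor is reported under the assigned arm. A subject could then be a PtGA responder at Week 16 while EASI and vIGA from that visit are treated as missing. SCORAD and BSA could disagree with EASI for a reason unrelated to RPT193. The stake is the consistency and readability of the descriptive results at Weeks 12 and 16.

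**Working it through.** No stated figure is in question, so the main check compares the texts.

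**1. Where the SAP gives a post-rescue rule**

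| Place | Endpoints covered |
|---|---|
| SAP II.A, estimand | EASI, vIGA, PP-NRS |
| SAP IV.D.2, including treatment-failure and control-based imputation | Same three scores; PtGA is not in the treatment-failure list |
| SAP VI.C and VI.D.1, MMRM | EASI, PP-NRS |
| SAP VI.D.2, time-to-event censoring | EASI, PP-NRS |
| SAP VI.E, through Week 16 | None |
| SAP VI.E, Weeks 18–24 | Durability endpoints only |

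**2. Which visits are exposed.** Need for topical treatment before Day 57 means withdrawal, so Weeks 2 and 4 carry no rescue data. Rescue opens on Day 57, the Week 8 target day, so Week 8 is barely touched. That leaves Weeks 12 and 16. POEM, DLQI, skin pain, ADSS, ACQ-5 and the change scores for PtGA and sleep VAS are listed for Week 16 only.

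**3. Size for PtGA response (illustration).** The documents give neither a rescue rate nor a response rate after rescue. Assume rescue of r_p = 10–30% on placebo and r_a = 5–20% on active, and q = 20–40% PtGA response after rescue. Counting those responses instead of non-response:
- raises placebo by r_p × q, from 0.10 × 0.20 = 2 to 0.30 × 0.40 = 12 points;
- raises active by r_a × q, from 0.05 × 0.20 = 1 to 0.20 × 0.40 = 8 points;
- moves the difference by (r_a − r_p) × q, from (0.05 − 0.30) × 0.40 = −10 to (0.20 − 0.10) × 0.40 = +4 points.

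The sign follows whichever arm uses more rescue.

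**4. Size for a continuous percent change (illustration).** Assume 20% rescue on placebo, 12% on active, and a gain of 20–40 points after rescue. The difference shrinks by (0.20 − 0.12) × 20 = 1.6 to (0.20 − 0.12) × 40 = 3.2 points.

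**5. Would deleting the values cure it?** Keep 20% and 12% rescue. Assume rescued subjects would otherwise show 0% improvement, unrescued placebo subjects improve 40%, and unrescued active subjects improve m%.
- Placebo mean with everyone counted: 0.80 × 40 = 32. After deletion: 40, a rise of 8.
- Active mean with everyone counted: 0.88m. After deletion: m, a rise of 0.12m.
- The difference shrinks by 8 − 0.12m, which is 3.2, 2.0 or 0.8 points for m = 40, 50 or 60.

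This is of the same order as step 4. Blanking without imputation replaces one distortion with another.

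**The case against.** A reader might infer that the SAP has decided to credit rescue benefit to the assigned arm and will thereby hide a treatment difference. The documents do not support that. VI.E is silent; it does not say that post-rescue values count. The SAP's observed-cases definition in IV.D.2 also imputes nothing and blanks data after rescue, and a programmer could borrow it. The direction is not settled either, because rescue could be more frequent on active.

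The conflict is also not purely between SAP and protocol. Protocol 9.4.5 limits blanking to primary and key secondary endpoints, and 9.4.4 asks only for description. The SAP is compatible with both.

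The effect may be modest as well. With 60 per arm and an assumed 20% PtGA response, the standard error of a difference is √(2 × 0.20 × 0.80 / 60) = 7.3 points, and no test is planned for these endpoints. SAP VII.G already summarises incidence, duration and time to first rescue.

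These points limit the concern but do not remove it. VI.E does not cite observed cases, and that definition sits under a heading for other scores. Even if it were borrowed, PtGA would be missing rather than non-response, and continuous values would be blank rather than imputed, so 6.6.4 would still not be met. The rescue summaries show how much rescue was used, not how it entered each endpoint.

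**Conclusion.** The gap is real and minor. SAP VI.E lacks a post-rescue rule through Week 16 that Protocol 6.6.4 expects for every efficacy endpoint. Protocol 9.4.5 does not match 6.6.4 in scope, and SAP I.C does not record the departure. Followed literally, VI.E counts PtGA responses reached on rescue at Weeks 12 and 16.

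Under the assumed ranges the PtGA difference moves by −10 to +4 points, and a continuous difference by about 1.6 to 3.2 points at 20% versus 12% rescue. Both rest on rescue rates and post-rescue gains that the documents do not give, so neither size nor direction can be asserted. The affected results are exploratory and descriptive; the primary and key secondary analyses have their own rule and are untouched.

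**What to change.** 1. Add to SAP VI.E that a subject who starts rescue is a PtGA non-responder at all later visits through Week 16, as 6.6.4 requires.
2. For the continuous and shift-table summaries, state one post-rescue rule that agrees with 6.6.4. Values would be imputed, for example by extending the control-based multiple imputation, LOCF or WOCF already defined in the SAP, and the no-imputation sentence in VI.E would be amended to match. Otherwise, list the departure in SAP I.C. Either way, show the as-observed values and the number rescued by arm and visit beside each summary.
3. Reconcile Protocol 6.6.4 with 9.4.5 so that one scope applies.

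The cost is a few sentences and slightly more programming; the rescue start date is already needed for EASI. If the sponsor only blanks the values, there is a further cost. The Week 12 and 16 samples become smaller and selected, because rescue before Day 113 requires documented EASI no better than baseline over two consecutive visits, so the subjects removed are known non-improvers. SAP I.B allows changes until unblinding, and the rule should be fixed before then.

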#### C. Sample Size Predictions

- [Redacted]
- [Redacted]
- [Redacted]
- [Redacted]

Based on the assumptions above and using a two-sample t-test, a sample size of 60 subjects per treatment group is needed to detect the treatment effect on the primary endpoint between RPT193 and placebo. Assuming a 10% drop out rate, a total sample size of 268 subjects (67 per treatment group) will be needed.

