## **G. Multiple Comparisons**

For the primary efficacy endpoint of percent change from baseline in EASI at Week 16, to preserve the Type I error at 0.05, a serial gatekeeping strategy will be employed to address the multiplicity of the pairwise comparison of each RPT193 dose group vs. placebo. The order of the testing will be performed from the RPT193 400mg, 200mg to 50mg. Dose comparisons for percent change from baseline in EASI at Week 16 will stop when non-significance (2- sided p-value  $\geq 0.05$ ) is observed.

Analyses of secondary and exploratory endpoints will be presented without adjustment for multiplicity.

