## I. Subgroups

The following subgroups will be considered for primary and key secondary analyses for descriptive purposes:

- Prior treatment with dupilumab or tralokinumab (Yes or No)
- Prior treatment with JAK inhibitor (Yes or No)
- Baseline EASI score (<21 or ≥21)
- Baseline EASI score (<median or ≥median)
- Baseline %BSA of AD affected skin (<50% or ≥50%)

- Baseline %BSA of AD affected skin (<median or ≥median)
- Baseline vIGA score (3 or 4)
- Baseline peak pruritus NRS (<7, ≥7, <median or ≥median)
- Age group (<median or ≥median)
- Sex (Male or Female)
- Race (White or Others, Asian or Others)
- Atopic dermatitis disease duration (< median years, ≥median years). The duration for patients with ongoing AD will be from the start date to the randomization date.
- Atopic comorbidities (food allergy (immediate type), allergic rhinitis, or asthma) (Yes or No)
- Baseline weight group (<70 kg, ≥70-<100 kg, ≥100 kg)
- BMI (<15, ≥15-<25, ≥25-<30, ≥30)

If the number of subjects is too small within a subgroup, then the subgroup categories may be redefined before unblinding the study.

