### C. Primary Efficacy Analysis

The primary endpoint is the percent change in EASI from baseline to Week 16. The primary analysis will be based on the FAS and will use control-based PMM-MI to handle missing data.

The primary efficacy endpoint will be analyzed with an ANCOVA model. The model will include treatment group (each RPT193 dose vs. placebo), the randomization stratification factors of baseline vIGA score (3,4), and prior dupilumab or tralokinumab use (yes or no), and baseline EASI score as a covariate.

For each imputed dataset the least square (LS) mean, and LS mean difference in the percent change from baseline between each RPT193 dose level and placebo along with the corresponding estimated standard error will be reported. These results will be combined in PROC MIANALYZE using Rubin's formula and the resulting p-value will be used for inference at the 0.05 level of significance. The LS mean and LS mean difference along with the 95% confidence interval (CI) and p-value will be reported.

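### The SAP gives the EASI subgroups unimputed arm-by-arm summaries, while the primary analysis of the same variable uses control-based imputation and an adjusted difference from placebo

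*SAP*

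**What the plan says.** SAP VI.E opens with a rule for everything it lists: the FAS is used, and "Descriptive summary statistics will be provided by treatment and visit for exploratory endpoints listed below. No imputation will be utilized for missing data". One listed item is "Subgroup analysis of the primary efficacy endpoint as outlined in section IV.I". SAP IV.I, to which that item points, says: "The following subgroups will be considered for primary and key secondary analyses for descriptive purposes". It names the subgroups but gives no model, contrast, confidence interval or missing-data rule.

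For the same variable in the whole FAS, SAP VI.C says: "The primary analysis will be based on the FAS and will use control-based PMM-MI to handle missing data". The analysis is an ANCOVA reporting an LS-mean difference for each dose against placebo, with a 95% CI and p-value.

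Two smaller mismatches sit alongside this:

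- Ethnicity is a named subgroup in Protocol Table 1 and in SAP II but is missing from the IV.I list. SAP I.C declares that the CCL17/22 subgroups moved to another plan and says nothing about Ethnicity.
- IV.I covers the primary and key secondary endpoints; VI.E covers only the primary.

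**The concern.** Efficacy in subpopulations is a stated exploratory objective, and the protocol says the data will inform the design of pivotal studies. Under VI.E the output for that objective is four separate arm summaries per subgroup, with no estimate of effect.

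The summaries also rest on a different missing-data basis from the headline result. Protocol 6.6.4 allows rescue from Day 57 to Week 16 only after EASI has been no better than Baseline at two consecutive visits, and SAP IV.D.2 sets scores after rescue to missing. Subjects who need the named topical therapies before Day 57 are withdrawn from the study. Both routes remove subjects who are doing badly. Unimputed arm means therefore describe a selected group, and a gap between a subgroup and the primary estimate may reflect method rather than a real difference in effect.

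**Working it through.** **Plan's own figure.** SAP III.C says "a sample size of 60 subjects per treatment group is needed to detect the treatment effect on the primary endpoint", with 10% dropout. 60 / 0.9 = 66.7, rounded up to 67; 67 × 4 = 268. This matches the SAP. The effect, SD and power behind the 60 are blacked out, so no bias in EASI points can be derived from the documents. Missing shares, gaps and effects below are assumptions.

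**Notation.** m_a and m_p are the shares missing at Week 16 on active and placebo. g is how many points worse the missing subjects are than the observed ones. D is the observed active-minus-placebo difference in improvement.

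**1. Arm means.** Observed mean minus full-data mean = m × g.
- 10% missing, g = 20: 0.10 × 20 = 2 points too favourable.
- 30% missing, g = 40: 0.30 × 40 = 12 points too favourable.

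**2. Contrast against each arm's own full data.** The full-data difference is D + (m_p − m_a) × g.
- Equal missingness and equal gap: no bias.
- m_p = 20%, m_a = 10%, g = 10 to 40: the observed contrast is too small by 0.10 × g = 1 to 4 points.
- m_p = 10%, m_a = 20%: too large by the same 1 to 4 points.

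A simulation gave the same pattern. It assumed 67 per arm, a true difference of 20, SD 35, correlation 0.6 between Weeks 12 and 16, and the worst Week 12 subjects missing. The observed difference was 20.0 with 10% missing in both arms, 17.1 with 20% placebo and 10% active, and 15.2 with 30% and 15%.

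**3. Contrast against a simplified control-based method.** Suppose missing subjects in both arms are imputed g points worse than the observed placebo mean. The control-based difference is then D(1 − m_a) + (m_p − m_a) × g, so observed minus control-based = m_a × D − (m_p − m_a) × g.
- Equal missingness, D = 20: the control-based difference is 18, 16 or 14 at 10, 20 or 30% missing. The observed contrast is larger by 2, 4 or 6 points.
- m_p = 20%, m_a = 10%, D = 20: the gap is 2 − 0.10 × g. It is +2 at g = 0, zero at g = 20 and −2 at g = 40.

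The sign depends on quantities the documents do not give. The SAP's regression also conditions on earlier visits, so these figures only show how the gap behaves.

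**4. Precision in the smallest stratified subgroup.** Protocol 6.3 caps prior dupilumab or tralokinumab use at about 20%: 67 × 0.20 = 13.4 per arm. The 95% CI half-width for a difference (normal approximation) is 1.96 × √(2/13.4) = 0.76 SD, or 0.80 SD with 10% missing (12.1 per arm). With 60 per arm and two-sided alpha 0.05, the detectable effect is (1.96 + 0.84) × √(2/60) = 0.51 SD at an assumed 80% power and (1.96 + 1.28) × √(2/60) = 0.59 SD at 90%. The interval in this subgroup would be wider on each side than the effect the trial is sized for.

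**5. Imputation model against subgroup list.** The Appendix II example code for EASI uses baseline EASI, earlier visits, treatment, baseline vIGA and prior dupilumab/tralokinumab use. IV.I contains 13 distinct variables. Three are in the model (baseline EASI, baseline vIGA, prior use); the other ten, such as sex, race, age and BMI, are not.

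**The case against.** **Descriptive reporting is planned.** Protocol 9.4.4 says exploratory endpoints are summarised descriptively, and IV.I says the same of subgroups. This stands: there is no departure from the protocol and no call for subgroup testing. It does not settle the missing-data rule. SAP VI.D.2 summarises the other secondary endpoints descriptively and still imputes them, and an estimate with a nominal CI is also descriptive.

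**The text may be ambiguous rather than wrong.** The no-imputation rule introduces a mixed list. The subgroup item defers to IV.I, which speaks of the primary and key secondary analyses, and IV.D.2 imputes EASI through Week 16. The sponsor may have meant the primary method to carry over. VI.E also does not itself say whether scores after rescue are dropped; that comes from IV.D.2. If they were kept, the subgroups would mix in rescue effects and again depart from the primary estimand. Either reading needs the wording settled.

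**Subgroups could still be compared.** Under IV.J continuous summaries include n, mean and SD, so a reader could work out an unadjusted difference and CI. An observed-case ANCOVA in the whole FAS is also planned, giving a benchmark on a similar missing-data basis. This stands, so it would be too strong to say that comparison is impossible.

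**Tempting stronger reading.** A reader might infer that subgroup effects will look smaller than the primary result and that a benefiting subgroup will be missed. The documents do not support this. It needs more missingness on placebo and a large enough gap; steps 2 and 3 show zero or reversed bias under other plausible values.

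**Conclusion.** The point holds in limited form. As written, the same variable is handled by two methods, and the subgroup version gives no dose-placebo difference for a stated objective. Because rescue depends on poor EASI, observed arm means will tend to be too favourable: 2 to 12 points under assumed 10 to 30% missing and a 20 to 40 point gap. Subgroup results will not correspond to the primary estimate, but the size and direction of the effect on the contrast cannot be fixed from the documents.

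The primary conclusion is untouched, and so is the dose-order testing intended "to preserve the Type I error at 0.05, a serial gatekeeping strategy will be employed". The undeclared loss of Ethnicity and the different endpoint scope in IV.I and VI.E are minor but plain on the text. This is an inexpensive improvement worth making before unblinding, not a threat to the trial.

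**What to change.** - In SAP IV.I and VI.E, exempt the subgroup analysis of percent change in EASI from the no-imputation rule. State that it uses the primary control-based imputation approach, with scores after rescue handled as in the primary analysis, and the primary ANCOVA within each subgroup. Drop any term that is constant there, such as baseline vIGA in the vIGA subgroups.
- Report the nominal LS-mean difference for each dose against placebo with its 95% CI, and make no significance claim.
- Either add the subgroup variable to the imputation model, or reuse the 100 primary datasets and state as a limitation that their model omits most subgroup variables and may pull subgroup estimates together.
- Restore Ethnicity to IV.I, or declare its removal in I.C.
- Make IV.I and VI.E agree on whether key secondary endpoints are included.

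The cost is SAP wording and modest programming, plus further imputation runs if subgroup variables are added. Small subgroups will show wide intervals: about 0.76 to 0.80 SD on each side at roughly 13 per arm. That is a fair picture of what such a subgroup can tell.
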